11.3 Treatment Assignment Procedures

Participants from all four cohorts will be assigned to treatment arm 1. All cohorts will open immediately.

11.3.1 Vaccine-Naïve Cohorts:

| Number | Description |
|--------|--|
| 1 | Hematologic Low Immunosuppression |
| 2 | Hematologic Intermediate Immunosuppression |
| 3 | Hematologic High Immunosuppression |
| 4 | Solid Tumor |

11.3.2 Booster Vaccine Cohorts:

| Number | Description |
|--------|--|
| 5 | CLL Not On Active Therapy |
| 6 | CLL Receiving BTK Inhibitor Interruption |
| 7 | CAR T Cell Therapy |
| 8 | Solid Tumor on PD1/PDL1 Inhibitor |
| 9 | Post Allogeneic Transplant |
| 10 | Other Hematologic Malignancy |
| 11 | Other Adult Solid Tumor |

11.3.3 Arm

| Name | Description |
|-------|--|
| Arm 1 | 100 mcg (0.5 mL) mRNA-1273 injection (IM) on days 1 and 29; with option for subsequent booster dose, 100 mcg (0.5 mL) mRNA-1273 injection (IM) no less than 4 weeks after day 29 |
| Arm 2 | 100 mcg (0.5 mL) mRNA-1273 injection (IM) on day 1 |

11.4 Final Analysis Plan

11.4.1 Populations for Analyses

11.4.1.1 Full Analysis Set

The Full Analysis Set (FAS) consists of all participants who a) receive at least one study injection, b) have baseline (Day 1) data available for those analyses that require baseline data, and c) have at least one post-injection assessment for the analysis endpoint.

11.4.1.2 Per-Protocol Set

The Per-Protocol (PP) Set consists of all FAS participants who meet all of the following criteria:

- Complied with the injection schedule.

- Complied with the timings of immunogenicity blood sampling to have post-injection results available for at least one assay component corresponding to the immunogenicity analysis objective.
- Have had no major protocol deviations that impact immune response during the period corresponding to the immunogenicity analysis objective.

The PP Set will serve as the primary set for the analysis of immunogenicity data in this study.

11.4.1.3 **Solicited Safety Set**

The Solicited Safety Set consists of all participants who received at least one study injection, and contribute any solicited AR data; i.e., have at least one post-baseline solicited safety assessment. The Solicited Safety Set will be used for the analyses of solicited ARs.

11.4.1.4 **Safety Set**

The Safety Set consists of all participants who received at least one study injection. The Safety Set will be used for analysis of safety except for the solicited ARs.

11.4.2 **Statistical Analyses**

11.4.2.1 **Immunogenicity Analyses**

The analyses of immunogenicity will be based on the PP Set. If the number of participants in the FAS and PP Set differ (defined as the difference divided by the total number of participants in the PP Set) by more than 10%, supportive analyses of immunogenicity may be conducted using the FAS.

For the primary immunogenicity endpoint, geometric mean titer (GMT) of specific bAb with corresponding 95% CI at each timepoint and geometric mean fold rise (GMFR) of specific bAb with corresponding 95% CI at each post-baseline timepoint over pre-injection baseline at Day 1 will be provided. Descriptive summary statistics including median, minimum, and maximum will also be provided.

For the secondary immunogenicity endpoint, GMT of specific nAb with corresponding 95% CI at each timepoint and GMFR of specific nAb with corresponding 95% CI at each post-baseline timepoint over pre-injection baseline at Day 1 will be provided. Descriptive summary statistics including median, minimum, and maximum will also be provided. For summarizations of GMT values, antibody values reported as below the LLOQ will be replaced by $0.5 \times \text{LLOQ}$. Values that are greater than the upper limit of quantification (ULOQ) will be converted to the ULOQ.

The number and percentage of participants with $\text{GMFR} \geq 2$, $\text{GMFR} \geq 3$, and $\text{GMFR} \geq 4$ of serum SARS-CoV-2-specific nAb titers and participants with seroconversion due to vaccination from baseline will be provided with 2-sided 95% CI using the Clopper-Pearson method at each post-baseline timepoint. Seroconversion at a participant level is defined as:

- For subjects with no detectable antibody titer ($< \text{LOD}$) at baseline: post-vaccination titer $\geq \text{LLOQ}$
- For subjects with a positive baseline titer ($> \text{LOD}$): post-vaccination titer ≥ 4 times the LLOQ

- For subjects with a baseline titer \geq LLOQ: post-vaccination titer \geq a 4-fold rise compared with baseline titer

GMT with corresponding 95% CI will be provided (for each group) at each time point. The 95% CI will be calculated based on the t-distribution of the log-transformed values and transformed back to the original scale for presentation.

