3.2 Study Objectives and Endpoints

| Objectives and Endpoints | |
|--|--|
| Primary Objective | Primary Endpoints |
| Safety Objective: To evaluate the safety and reactogenicity of the mRNA-1273 vaccine administered in 2 doses 28 days apart, in participants who have a | Safety Endpoints: 
Solicited local and systemic Adverse Reactions (ARs) through 7 days after each injection. |

| Objectives and Endpoints | |
|--|---|
| Primary Objective | Primary Endpoints |
| hematological malignancy and are immunosuppressed due to their disease and/or treatment, or receiving a PD-1/PDL-1 inhibitor for treatment of a solid tumor for participants who are vaccine- naïve. To evaluate the safety and reactogenicity of booster doses of mRNA-1273 vaccine administered to participants with cancer who have previously received an mRNA or alternative vaccine regimen | 
Unsolicited AEs through 28 days after each injection.SAEs throughout the entire study period.Vital sign measurements and physical examination findings. |
| Immunogenicity Objective: To assess the immunogenicity of mRNA-1273 in participants with cancer, as assessed by the titer or level of specific binding antibody (bAb) | Immunogenicity Endpoints: 
Titer or level of specific binding antibody (bAb), in participantsTiter or level of SARS-CoV-2-specific binding antibody (bAb) measured by ELISA on Day 1, Day 29, Day 36, Day 57 Day 209 and Day 394 for participants on Vaccine-Naïve CohortsTiter or level of SARS-CoV-2-specific binding antibody (bAb) measured by ELISA on Day 1, Day 29, Day 180, Day 360 for participants on Booster Vaccine Cohorts |

| Secondary Objective | Secondary Endpoints |
|---|--|
| To evaluate the immunogenicity of the mRNA-1273 vaccine administered, as assessed by the titer or level of neutralizing antibody (nAb). | For Vaccine-Naïve Cohorts: 
Titer or level of SARS-CoV-2-specific neutralizing antibody (nAb) on Day 1, Day 29, Day 36, Day 57, Day 209, and Day 394Seroconversion due to vaccination on Day 29, Day 36, Day 57, Day 209, and Day 394 measured as:
For subjects with no detectable antibody titer (< |

| Secondary Objective | Secondary Endpoints |
|---------------------|---|

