4.5 Study Treatment Compliance

All doses of the investigational study product (IP) will be administered at the study site by medically qualified study personnel and appropriately recorded (date and time) in the participant's medical records. If a participant does not receive vaccine, does not receive a full dose of vaccine, or does not receive all of the planned doses, the reason for the missed or partial dose will be recorded.

Participants in the vaccine-naïve cohorts who miss the second dose of IP due to noncompliance with the visit schedule and not due to a safety pause will still be required to follow the per protocol visit and testing schedule. Unless consent is withdrawn, a participant who withdraws or is withheld from receiving the second dose of study vaccine, if in the vaccine-naïve cohorts, will remain in the study and complete all safety and immunogenicity assessments required through the participant's scheduled end of study. The study site is responsible for ensuring that participants comply with the study windows allowed.

If a participant misses a visit, every effort should be made to contact the participant and complete a visit within the allowed visit window (Study Calendar, Appendix insert). If a participant does not complete a visit within the time window, that visit will be classified as a missed visit and the participant will continue with subsequent scheduled study visits. All safety requirements of the missed visit will be captured and included in the subsequent visit (e.g., clinical laboratory testing, memory aids review for reactogenicity, immunologic testing, as applicable).

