6.3.1 Criteria for removal from study treatment

- Participant requests to be withdrawn
- Unacceptable toxicity
- Allergic reactions, hyperimmune responses and/or SAEs considered related to the vaccine
- Participant becomes pregnant
- Investigator decision

The investigator should be explicit regarding study follow-up (e.g., safety follow-up) that might be carried out despite the fact the Participant will not receive further study product. If the Participant consents, every attempt will be made to follow all AEs through resolution. The procedures that collect safety data for the purposes of research must be inclusive in the original informed consent or the investigator may seek subsequent informed consent using an IRB-approved consent form with the revised procedures.

The investigator will inform the Participant that already collected data will be retained and analyzed even if the Participant withdraws from this study.

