7.3.2.1 Endpoint Assay Biospecimen Collection for Vaccine-Naïve Cohorts

| Test/Assay | Volume blood** (approx) | Type of tube** | Collection point* | Location of specimen analysis |
|---|----------------------------|-------------------|---|-------------------------------------|
| Serological Immunogenicity Assays | 5-10 mL (for plasma) | EDTA | D1, 29, 36, 57, 394, at COVID-19 infection*** | NIH [name] Lab |
| Neutralization assay using a wild-type SARS-CoV-2 | 3 mL (for serum) | SST | D1, 29, 36, 57, 209, 394, at | |

| Test/Assay | Volume blood** (approx) | Type of tube** | Collection point* | Location of specimen analysis |
|------------|----------------------------|-------------------|--------------------------|-------------------------------------|
| | | | COVID-19 infection*** | |

* See study calendar for collection windows. Sample collection should occur prior to vaccine administration on applicable days (i.e., D1 and D29). Participants who opt to receive a booster vaccine will have their samples drawn according to the Booster Vaccine Cohort calendar.

**Tubes/media may be adjusted at the time of collection based upon materials available if approved by the PI/laboratory investigator

***If a participant tests positive for COVID-19 while on study these labs will be collected within 2 weeks of a positive PCR test. A second post-infection blood collection will occur 2-4 weeks after this initial blood draw. These post-infection blood draws are optional.

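### In the vaccine-naïve cohorts, the undated injection-schedule criterion takes valid pre-Dose 2 samples out of the primary Day 29 estimates because of what happens afterwards

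*Combined protocol and SAP*

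**What the plan says.** Section 11.4.1.2 defines a single PP Set, and a member must meet all three of its criteria.

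- The first is "Complied with the injection schedule". It carries no visit or time limit.
- The second, on blood-sampling times, is tied to the analysis objective.
- The third is limited in time: "Have had no major protocol deviations that impact immune response during the period corresponding to the immunogenicity analysis objective".

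The same section states its role: "The PP Set will serve as the primary set for the analysis of immunogenicity data in this study". Section 11.4.2.1 then asks for GMT at each timepoint, and for GMFR and seroconversion at each post-baseline timepoint.

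For Arm 1 the schedule is two injections, on Days 1 and 29 (Section 11.3.3). Day 29 is a listed timepoint for the primary binding-antibody endpoint and for the secondary neutralizing-antibody and seroconversion endpoints (Section 3.2). The footnote to the sampling table in Section 7.3.2.1 puts the draw ahead of the injection: "Sample collection should occur prior to vaccine administration on applicable days (i.e., D1 and D29".

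Section 4.5 says that, unless consent is withdrawn, a vaccine-naïve participant who withdraws or is withheld from Dose 2 "will remain in the study and complete all safety and immunogenicity assessments required through the participant's scheduled end of study".

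The FAS (Section 11.4.1.1) needs only one injection. If FAS and PP differ by more than 10% of the PP number, "supportive analyses of immunogenicity may be conducted using the FAS" (Section 11.4.2.1).

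**The concern.** At Day 29 a vaccine-naïve participant has had one dose, and the sample measures the response to that dose. Whether Dose 2 follows cannot alter the sample, yet under the undated criterion it decides whether the result counts in the primary analysis. Two things are at stake.

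First, the trial pays to collect one-dose results under Section 4.5 and then leaves them out of the primary estimate.

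Second, the Day 29 estimate is conditioned on a later event that may be related to immune status. Section 6.3.1 stops vaccination for, among other reasons, "Allergic reactions, hyperimmune responses and/or SAEs considered related to the vaccine". Appendix E stops it after myocarditis or pericarditis but continues follow-up. Section 4.2.2 refers eligibility for a further dose to Section 5.1, which sets minimum lymphocyte and neutrophil counts. Section 6.1.2.2 says the Day 29 laboratory results are not reviewed before dosing, so how that gate operates is unclear. None of this proves a link with titer, but it makes one plausible.

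The study tests no hypothesis (Section 11.1), so the estimates are its result. Section 2.4.1 ties them to whether patients with cancer should be prioritised for vaccination or kept isolated.

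**Working it through.** **1. The plan's own total.** Vaccine-naïve: 4 × 20 = 80 (Table 1). Booster: 20 + 20 + 30 + 20 + 20 + 20 + 10 = 140 (Table 2). Together 220, which matches Section 11.2. (Section 3.1 gives 120 in six booster cohorts; this touches only the pooled line in step 3.) The point concerns the 80. The booster arm has one injection, on Day 1, so no scheduled dose follows its Day 29 sample.

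**2. Who is affected.**

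| Vaccine-naïve participant | Valid Day 29 sample? | Primary Day 29 analysis, criterion as written | Criterion limited to doses already due |
|---|---|---|---|
| Sampled, Dose 2 on schedule | Yes | In | In |
| Sampled, Dose 2 withheld or declined | Yes | Out | In |
| Sampled on time, Dose 2 given later, out of window | Yes | Out | In |
| Did not attend the Day 29 visit | No | Out | Out |
| Left the study before Day 29 | No | Out | Out |

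Only the second and third rows change. The third also depends on the window: Section 4.2.2 allows three days either side of Day 29, while Section 6.1.2.2 and Appendix F allow only a delay of up to three days. Those passages must be reconciled before compliance can be judged.

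**3. When the FAS analysis would be considered.** With N in the FAS and m of them outside the PP Set, the plan's measure is m/(N − m), which must exceed 10%. Here every enrolled participant is assumed to be in the FAS. Exclusions for other reasons would also count towards m.

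| Level at which the rule is applied | Largest m that does not trigger | Smallest m that triggers |
|---|---|---|
| One cohort, N = 20 | 1: 1/19 = 5.3% | 2: 2/18 = 11.1% |
| Vaccine-naïve arm, N = 80 | 7: 7/73 = 9.6% | 8: 8/72 = 11.1% |
| All participants, N = 220 | 20: 20/200 = 10.0% | 21: 21/199 = 10.6% |

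The plan does not say which row applies. If the rule is pooled over 220, all 20 exclusions could be vaccine-naïve, 20/80 = 25% of that group, with no FAS analysis called for.

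**4. How far an estimate could move.** The documents give no missed-dose rate and no titers for those not re-dosed, so the following is an assumption, shown in both directions. Take one cohort of 20, all with valid Day 29 samples, of whom 12 respond: 12/20 = 60% (Clopper-Pearson 95% CI 36% to 81%).

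| Not re-dosed | PP rate if all are non-responders | PP rate if all are responders |
|---|---|---|
| 2 | 12/18 = 67% | 10/18 = 56% |
| 4 | 12/16 = 75% | 8/16 = 50% |

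For the GMT, if the excluded have f times the GMT of those retained, the ratio of the PP GMT to the GMT of all 20 is (1/f)^(m/20). With f = 1/10 it is 1.12, 1.26 and 1.58 for m = 1, 2 and 4. With f = 4 it is 0.93, 0.87 and 0.76. With f = 1 it is 1: data are lost but there is no bias.

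**The case against.** The strongest reply has four parts.

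**The FAS already covers this.** A participant with one injection and a Day 29 result belongs to the FAS, so a reader who infers that the plan loses these data altogether goes too far. That stands. What remains is that the FAS analysis is supportive, optional even when triggered, and tied to a threshold whose level is not given.

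**The exclusion is inferred.** The plan nowhere says that missing Dose 2 removes a participant from every visit. That reading follows from one undated criterion, one PP Set and reporting at each timepoint. Because the other two criteria refer to the analysis objective, a visit-specific reading is possible. This also stands, but it leaves membership to be settled by interpretation, possibly after titers are known in an open-label trial.

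**Many who miss Dose 2 have no Day 29 sample.** Dose 2 and the Day 29 draw belong to the same visit, and the reason Section 4.5 names first is noncompliance with visits. A reader might equate the affected group with everyone who misses Dose 2. The documents do not support that, and the repair cannot recover samples never taken.

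**The regimen has two doses.** A completer set suits that regimen from Day 36 onward. This is accepted, and the point is confined to Day 29. No objective names a one-dose response, but Day 29 is a listed endpoint timepoint and will be reported.

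**Conclusion.** The point holds as a defect of wording with a limited reach. It affects the primary Day 29 GMT, GMFR and seroconversion in the vaccine-naïve cohorts, at most 80 of 220 participants, and only those who gave a valid sample and were then not given Dose 2, or were given it out of window.

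A reader might infer that the Day 29 response will be overstated because only the fitter participants are re-dosed. The documents do not support this. Dose 2 can also be missed through noncompliance or participant choice, and removal after strong reactions could act the other way. Even that is conjecture, since nothing defines a hyperimmune response as a high titer. If receipt of Dose 2 is unrelated to the Day 29 titer, there is no bias, only lost data.

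A reader might also size the effect from the CLL response rates in Section 2.4.5. Those compare treatment-naïve patients with patients on a BTK inhibitor after a different vaccine, and say nothing about people given or not given Dose 2.

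Direction and size therefore remain unknown. Under the assumed 12/20, four exclusions could move the estimate to anywhere from 50% to 75%, within the 36% to 81% interval that a cohort of 20 gives in any case. What is established is that the criterion sets aside usable data, and that the backstop need not operate.

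**What to change.** In Section 11.4.1.2, extend the first criterion so that after "Complied with the injection schedule" it continues: *for all doses due before the sample being analysed*. Day 29 then requires only Dose 1, and Day 36 onward requires both doses.

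For Day 36 onward, add one table giving, by cohort, the number excluded for missing Dose 2, the reasons, and their Day 29 titers where available, beside the PP result.

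The cost is one clause and one table. No new samples are needed, because Section 4.5 already provides for them, and no clinical rule changes. The drawback is that the analysis set then varies by visit, so each immunogenicity table must state its N.

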| SOP | Standard Operating Procedure |
| SUSAR | Suspected Unexpected Serious Adverse Reaction |
| US | United States |
| WHO | World Health Organization |

PROTOCOL SUMMARY

Title: A Trial of the Safety and Immunogenicity of the COVID-19 Vaccine (mRNA-1273) in Participants with Hematologic Malignancies and Various Regimens of Immunosuppression, and in Participants with Solid Tumors on PD1/PDL1 Inhibitor Therapy, Including Booster Doses of Vaccine

Design of the Study: This is an open-label, multicenter clinical trial designed to evaluate the safety, reactogenicity and primary immunogenicity of the mRNA-1273 vaccine administered in 2 doses, 28 days apart, in participants who have hematological malignancy and are immunosuppressed due to their disease and/or treatment or receiving a PD-1/PDL-1 inhibitor for treatment of a solid tumor can be associated with appropriately high rates of development of neutralizing antibodies of mRNA-1273. The trial will also evaluate the safety, reactogenicity and immunogenicity after administration of additional “booster” doses of the vaccine.

Study Phase: 2

Study Population: For the vaccine-naïve cohorts, up to 80 participants will be enrolled.

- 20 participants with solid tumor malignancies who have initiated PD1/PDL1 inhibitor therapy as part of standard of care and are deemed to have a stable regimen without the need for any immunosuppressive therapy or corticosteroids.
- 60 participants with leukemia, lymphoma, multiple myeloma and participants post-allogeneic stem cell transplant will be enrolled based on their perceived risk of immunosuppression.

For the previously-vaccinated (also known as “booster”) cohorts, up to 140 participants will be enrolled for booster injections. All participants on the vaccine-naïve cohorts will have the option of receiving boosters; however, they will not count towards the maximum accrual goal for each of the booster groups. Note: All participants will be eligible to receive up to three (3) booster doses of vaccine on study.

- 20 participants with solid tumor malignancies who have initiated PD1/PDL1 inhibitor therapy as part of standard of care and are deemed to have a stable regimen without the need for any immunosuppressive therapy or corticosteroids.
- 20 participants with chronic lymphocytic leukemia who are not currently on any therapies
- 20 participants with chronic lymphocytic leukemia who are on BTK inhibitor therapy alone

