| | 
LOD) at baseline: post-vaccination titer \geq LLOQ
 
• For subjects with a positive baseline titer ($>$ LOD): post-vaccination titer \geq 4 times the LLOQ• For subjects with a baseline titer \geq LLOQ: post-vaccination titer \geq a 4-fold rise compared with baseline titer 
For Booster Cohorts:
 
• Titer or level of SARS-CoV-2-specific neutralizing antibody (nAb) on Day 1, Day 29, Day 57, Day 180, and Day 360• Seroconversion due to vaccination on Day 29, Day 36, Day 57, Day 180, and Day 360 measured as:
• For subjects with no detectable antibody titer ($<$ LOD) at baseline: post-vaccination titer \geq LLOQ• For subjects with a positive baseline titer ($>$ LOD): post-vaccination titer \geq 4 times the LLOQ• For subjects with a baseline titer \geq LLOQ: post-vaccination titer \geq a 4-fold rise compared with baseline titer |

| Exploratory Objective | Exploratory Endpoints |
|--|--|
| To assess immune responses against the SARS-CoV-2 nucleocapsid and spike proteins. | Immune responses against the SARS-CoV-2 nucleocapsid and spike proteins on Day 1, Day 29 and Day 57. |

| Exploratory Objective | Exploratory Endpoints |
|--|---|
| To evaluate salivary measurement of IgG antibodies against the SARS-CoV-2 nucleocapsid and spike (S) proteins. | Salivary measurement of IgG antibodies against the SARS-CoV-2 nucleocapsid and spike proteins on Day 1, Day 29, Day 36, Day 57, Day 209, and Day 394. |

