7.2 Concomitant Medications/Treatments

7.2.1 General

All ongoing medications and therapies at screening will be considered prior medications.

Concomitant medications will include all current medications and medications taken within the 30 days prior to enrollment (prescription and over-the-counter drugs, vitamins and supplements, topical products, and vaccinations) through 34 days after the second vaccination (approximately Day 57-60 for participants who receive both doses of vaccine or early termination (if prior to Day 60), whichever occurs first. Assessment of eligibility also will include a review of permitted and prohibited medications (per the exclusion criteria).

Administration of any concomitant medications, therapies or vaccines will be documented in the participant's medical record and eCRF.

Contraceptive status is assessed and documented at every scheduled clinic visit for participants who were born female and who are sexually active in a way that could lead them to becoming pregnant. Prior to enrollment and throughout the study, staff will ask participants to verbally confirm their use of effective contraceptive methods.

7.2.2 For Hematologic Malignancies Cohorts:

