7.3.2 Serological Immunogenicity Endpoint Assays

Blood samples for immunogenicity assessments will be collected before administration of study treatment. The following analytes will be measured:

- Serum bAb levels against SARS-CoV-2 as measured by ligand-binding assay specific to the SARS-CoV-2 S protein
- Serum bAb levels against SARS-CoV-2 as measured by ligand-binding assay specific to the SARS-CoV-2 nucleocapsid protein
- Serum nAb titer against SARS-CoV-2 as measured by pseudovirus and/or live virus neutralization assays

Serum will be tested using the ligand-binding assay specific to the SARS-CoV-2 nucleocapsid to determine the immunologic status of study participants at baseline and assess for seroconversion due to infection during the course of the study. Serum from a subset of participants will be tested in the other assays. The selection of the subset and timepoints to be tested are described in the statistical analysis plan. Sample aliquots will be designed to ensure that backup samples are available and that adequate vial volumes may allow for further testing.

The date of each sample collected will be recorded in the eCRF, and unique sample identification will be used to maintain the blind at the laboratory at all times and to allow for automated sample tracking and storage. Handling and preparation of the coded samples for analysis, as well as shipping and storage requirements, will be provided in a separate study manual.

The ligand-binding assay and measurement of nAb titers will be performed in [name] Lab, NIH.

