11 STATISTICAL CONSIDERATIONS

11.1 Study Hypotheses

There is no hypothesis testing in this study; the study is intended to develop modestly precise estimates of parameters which reflect potential efficacy.

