11.2 Sample Size Considerations

The number of proposed participants is considered sufficient to provide a descriptive summary of the immunogenicity and safety of mRNA-1273 with reasonable precision overall and in various cohorts of participants.

It will be assumed that there is a maximum of 220 participants available for evaluation, but that subsets of 20 and 30 participants may be considered as well, primarily based on the sub-cohorts for hematological malignancies. In addition, early results any cohort may be reported prior to final study completion after evaluation of day 57 lab results. Overall, there will be 20 evaluable participants with solid tumors and 60 participants with hematologic malignancies in the vaccine-naïve cohorts. The booster vaccine cohorts will have a maximum enrollment of 20 participants with the exception of the CAR T cell therapy cohort which will have a maximum enrollment of 30 participants and the Other Adult Solid Tumor cohort which has a maximum enrollment of 10 participants. Participants enrolled onto the vaccine naïve cohort who receive a booster dose will not be counted towards these totals.

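### No analysis rule separates infection from vaccination, so the per-protocol titers and the vaccine-attributed seroconversion count infection-induced antibody, although the data to detect infection are largely planned

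*Combined protocol and SAP*

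**What the plan says.** Section 11.4.1.2 builds the PP set from the full analysis set (FAS) with three conditions: compliance with the injection schedule, compliance with sampling times, and "Have had no major protocol deviations that impact immune response during the period corresponding to the immunogenicity analysis objective". Section 8.11 defines a deviation as non-compliance with the protocol or related documents. The FAS definition in 11.4.1.1 does not mention infection. Past infection is not an exclusion; the criterion that names SARS-CoV-2 (5.2.1) concerns exposure within 14 days.

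Section 11.4.2.1 reports GMT and GMFR for binding and neutralizing antibody, and "participants with seroconversion due to vaccination from baseline", at each post-baseline timepoint. The seroconversion rule uses titers relative to LOD, LLOQ and baseline and nothing else. Section 3.2 carries these endpoints to Day 394 (naïve) and Day 360 (booster).

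Section 7.3.2 gives the serum nucleocapsid assay the task of establishing baseline status and to "assess for seroconversion due to infection during the course of the study". The serology rows list Days 1, 29, 36, 57 and 394 for naïve cohorts (7.3.2.1) and Days 1, 8, 29, 57, 180 and 360 for booster cohorts (7.3.2.2). Extra draws at COVID-19 infection are optional.

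Section 7.2.1 collects concomitant medications, including vaccinations, "through 34 days after the second vaccination (approximately Day 57-60" for participants who receive both doses.

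**The concern.** An endpoint that names vaccination as the cause should have some means of setting aside antibody with another cause. The protocol has one: mRNA-1273 encodes only the spike protein (2.2), so a new nucleocapsid response points to infection. Yet section 11 uses nucleocapsid status for no analysis set, censoring rule, subgroup or sensitivity analysis. It reappears only as a descriptive exploratory objective (11.4.2.6).

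The exposure is greatest at the 6- and 12-month visits and in cohorts expected to respond poorly, where one or two infections can move a cohort of 20. Persistence of the vaccine response could be overstated, and apparent cohort differences could partly reflect exposure to the virus.

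Off-study spike vaccine and anti-spike antibody products raise the same problem by another route. Nucleocapsid testing cannot detect them, so they depend on a record, and the defined record ends about two months after the first naïve dose.

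**Working it through.** **Does the PP set remove infected participants?** Becoming infected is not non-compliance (8.11), nor does it breach the injection schedule or the sampling times. All three PP conditions can therefore be met, and the participant stays. The FAS also keeps them, and its supportive analysis is optional.

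**Are data available to detect infection late?** Largely yes.
- Naïve serology: Day 394 is listed; Day 209 is not, although 3.2 makes binding antibody a primary endpoint that day. The neutralization row does list a Day 209 serum sample.
- Booster serology: Days 180 and 360 are listed.
- Salivary IgG against nucleocapsid and spike: Days 209 and 394 (7.3.5) and Days 180 and 360 (7.3.6).

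**When does the medication window end?** Day 29 + 34 = Day 63, or Day 60 to Day 66 if dose 2 moves three days either way; the stated range is Day 57-60. The share of naïve follow-up after Day 63 is (394 − 63)/(394 − 1) = 84%. The base booster schedule has no second vaccination, so the cut-off has no clear meaning there. The visit lists name medication review on Days 1 and 29 (6.1.2.1, 6.1.2.2) and booster Day 1 (6.1.3.1), not at later visits.

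**The plan's own sample-size figure.** Section 11.2 states: "It will be assumed that there is a maximum of 220 participants available for evaluation". Naïve cohorts: 20 + 60 = 80. Booster cohorts: 20 + 20 + 20 + 30 + 20 + 20 + 10 = 140, as in the summary ("up to 140 participants will be enrolled for booster injections"). The total is 220, which reproduces. The point does not rest on it; cohort sizes of 20 and 30 are what matter below.

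**Illustrative size.** Infection share and titer rise are assumptions.

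GMT: if k of 20 participants have titers multiplied by f, the GMT is multiplied by f^(k/20).

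| k of 20 | f = 10 | f = 100 |
|---|---|---|
| 1 | 1.12 | 1.26 |
| 2 | 1.26 | 1.58 |
| 4 | 1.58 | 2.51 |

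The ULOQ cap in 11.4.2.1 would limit the f = 100 column.

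Seroconversion: observed rate = p + (1 − p)q, where p is the true vaccine rate and q is the share infected and converted by the visit. Coverage is the exact probability that the Clopper-Pearson 95% interval contains p. Two values of p come from the documents: 50% is the middle of the 40-60% anticipated after CAR T therapy (2.4.4), and 16% is the rate cited for continuous BTK inhibitor treatment with another vaccine (2.4.5), used only as a low-response case.

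| p | q | Observed | Coverage, n = 20 | Coverage, n = 30 |
|---|---|---|---|---|
| 50% | 0 | 50% | 95.9% | 95.7% |
| 50% | 5% | 52.5% | 95.4% | 94.9% |
| 50% | 10% | 55% | 93.8% | 92.6% |
| 50% | 20% | 60% | 87.3% | 82.3% |
| 16% | 10% | 24.4% | 90.9% | 82.4% |
| 16% | 20% | 32.8% | 68.0% | 45.6% |

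**The case against.** **Infection data.** A reader might infer from the exploratory endpoint, "nucleocapsid and spike proteins on Day 1, Day 29 and Day 57", that infection data stop at about two months. The documents do not support this. That endpoint does not say serum; it could equally mean the cell-based assay against spike and nucleoprotein peptides in 7.3.4, which naïve cohorts do not have after Day 57 except at COVID-19 infection. Section 7.3.2 plans nucleocapsid serology over the whole study, and the sampling tables reach the last visit. The calendar keys in Appendices F and G also ask participants for all information about a COVID-19 infection. This objection stands: the infection gap is mainly one of analysis.

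**Off-study products.** A reader might also infer that late vaccine doses and antibody products are invisible. That too goes beyond the text. The 6- and 12-month visits take an interim medical history and collect unsolicited adverse events, although 8.3 ends general adverse event collection 28 days after the last vaccination. Section 7.2.1 also has a sentence without an end date on documenting medications, therapies and vaccines. An off-study dose might be judged a breach of the injection schedule, but the criterion does not say so. What remains is that the record is not reliable and its end is unclear.

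**Importance.** Section 11.1 states: "There is no hypothesis testing in this study". No between-cohort contrast is specified, early reporting may follow Day 57, and small infection shares barely move coverage when p = 50%. Infection may also raise little antibody in some cohorts, as 2.4.4 notes after CAR T therapy. These points limit the severity. They do not remove the point, because estimates are the trial's only statistical output.

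**Censoring.** Removing post-infection samples is a choice of estimand. If low responders are infected more often, censoring removes them selectively and raises late GMTs. This stands, and is why the uncensored result must always be shown.

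**Conclusion.** The point holds as an omission in the analysis plan. As written, infected participants stay in the PP set and their post-infection titers enter GMT, GMFR and the seroconversion attributed to vaccination at every visit. The data for an infection rule are largely planned; the exceptions are the missing Day 209 serology entry and the optional post-infection draws. Separately, the medication and vaccine window ends at Day 63 by the protocol's own arithmetic and is undefined for booster cohorts, so late spike vaccine or anti-spike products are not reliably recorded.

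The size cannot be fixed from the documents. It is small if few participants are infected and p is near 50%; it becomes material with about 20% infected, large titer rises or low response rates. The coverage figures assume that infection converts a share q of those the vaccine did not. On this footing it should be corrected before analysis, but the evidence does not support calling it a defect that invalidates the trial.

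**What to change.** 1. **11.4.1.2 and 11.4.2.1.** In the PP immunogenicity analysis, exclude samples taken after the first of these events following study Day 1: a positive PCR; nucleocapsid seroconversion from a negative baseline; an off-study COVID-19 vaccine dose; or an anti-spike antibody or immunoglobulin product. The Day 1 start is essential: directly enrolled booster participants must already be vaccinated (5.2.3), and a rule without a start date would remove them all. On-study boosters are not meant, since 6.1.3 resets the calendar for them. Summarise participants who are nucleocapsid-positive at baseline separately. Always report the uncensored FAS result alongside.
2. **7.3.2.1.** Add Day 209 to the naïve serology row, and confirm that the serum nucleocapsid assay is run on the Day 209/394 and Day 180/360 samples.
3. **7.2.1.** Record COVID-19 vaccines and antibody products to the final visit in both arms, and restate the cut-off so that it is defined for booster cohorts.

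The cost is SAP text, an assay already in use, one eCRF question at existing visits, and somewhat fewer late PP samples.
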